2.4.2. Potential Risks

The initial clinical program for vibegron in the treatment of OAB includes subjects of both sexes. It is estimated that the ongoing Phase 3 program in OAB (RVT-901-3003 and RVT-901-3004) will include approximately 15% males, which will contribute to safety data comprising more than 200 men in addition to those enrolled in the URO-901-3005 and URO-901-3006 studies.

Based on aggregate preclinical, clinical pharmacology, and Phase 2 and 3 studies, AEs of special interest (AESIs) predefined for specific evaluations in vibegron clinical studies are as follows:

- Potential major cardiovascular events
- Hypertension
- AEs suggestive of orthostatic hypotension as confirmed by orthostatic vital signs
- AEs suggestive of cystitis or urinary tract infection
- Elevated aspartate transaminase (AST) or alanine transaminase (ALT) laboratory value requiring that the study drug be temporarily withheld or permanently discontinued
- Neoplasm

In addition, the risk for increases in post void residual urine volume and urinary volume will be closely monitored for post-void retention during the study. Study URO-901-3005 enrollment criteria will exclude men with PVR volume ≥ 100 mL at screening and at baseline and those with maximum urinary flow (Q_{max}) less than 5 mL/second. Post-void residual urine volume will be assessed throughout the study, and subjects with a single PVR volume of ≥ 300 mL or an AE of urinary retention will be withdrawn.

Prespecified definitions of urinary retention and other AESIs are provided in the Adverse Event of Special Interest section (Section 8.4.6). More detailed information about the known and expected benefits and risks from the study and reasonably expected AEs of vibegron may be found in the Investigator's Brochure.

[figure not shown]
3. Objectives and Endpoints

Assessments in Study URO-901-3006 are referenced to the initial Baseline (Visit 3) from Study URO-901-3005. Therefore, CFB study endpoints for Study URO-901-3006 are relative to Study URO-901-3005 baseline. At the Week 52 visit, CFB comprises 52 weeks of vibegron exposure for subjects randomized to vibegron in Study URO-901-3005 and 28 weeks of vibegron exposure for subjects randomized to placebo.

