7.1. Discontinuation of Study Drug

Subjects who discontinue study drug will complete the Week 52/Early Withdrawal assessments specified in the Schedule of Assessments (Section 1.3).

Reasons for discontinuation from the study drug include the following:

- Any AE of urinary retention
- Any occurrence of PVR volume \geq 300 mL

Discontinuation of study drug for abnormal liver function should be considered by the investigator when a subject meets all of the conditions outlined in Section 8.4.6.2 for Hy's law or if the investigator believes that it is in best interest of the subject (reason for discontinuation will be AE).

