7.2. Subject Discontinuation/Withdrawal from the Study

- A subject who discontinues study drug will also be withdrawn from the study.
- A subject may choose to withdraw from the study at any time at his own request, or may be withdrawn at any time at the discretion of the investigator for safety, behavioral, compliance, or administrative reasons.
- If a subject withdraws consent for disclosure of future information, the Sponsor or designee may retain and continue to use any data collected before such a withdrawal of consent.
- If a subject withdraws from the study, he may request destruction of any blood or urine samples taken and not tested, and the investigator must document this in the site study records.
- Subjects who withdraw from the study will not be replaced.

The Week 52/Early Withdrawal assessments will be completed when a subject withdraws or is withdrawn from the study, if possible (see Schedule of Assessments in Section 1.3).

Reasons for discontinuation from the study include the following:

- AE
- Lack of efficacy
- Noncompliance
- Withdrawal of consent
- Lost to follow-up
- Physician decision
- Protocol deviation
- Death
- Other

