8.4.6. Adverse Events of Special Interest

Selected nonserious and SAEs will be reported as AESIs. AESIs that also meet the definition of an SAE must be reported as described in Section 10.3.

Adverse events of special interest for this study include:

- Adverse events consistent with urinary retention
 - An AE of urinary retention should only be recorded when a subject has a raised PVR that requires intervention with clean intermittent catheterization (CIC) or temporary placement of a urinary catheter according to the following criteria:
 - a) subject has a PVR of ≥ 300 mL (regardless of symptoms), OR

b) subject has a PVR ≥ 200 mL and < 300 mL and the subject reports associated symptoms, ie, sensation of bladder fullness or inability to void despite persistent effort, that in the investigator's opinion require CIC.

Note: An AE of residual urine volume should be recorded if, in the investigator's opinion, the raised PVR is clinically significant but does not fulfill the above definition for urinary retention. As stated above in Section 7, subjects with a single PVR volume of ≥ 300 mL or an AE of urinary retention will be withdrawn from the study.

- Adverse events suggestive of cystitis or urinary tract infection (UTI)
 - An AE of UTI will be recorded if both the following criteria are fulfilled, regardless of subject symptoms:
 - a) a positive urine culture result with a bacteriuria count of $\geq 10^5$ CFU/mL
 - b) leukocyturia of ≥ 5 /hpfIf a subject meets the criteria for the definition of a UTI, the investigator will record whether the UTI was “symptomatic” or “asymptomatic” on the AE eCRF.

Note: If urinalysis/culture results are reported which, in the opinion of the investigator, are considered clinically significant but do not fulfill the above definition of a UTI, the findings should be recorded as AEs (eg, bacteriuria, leukocyturia).

- Potential major cardiac and cerebrovascular events, including death (or any event with fatal outcome), myocardial infarction, cerebrovascular accident, hospitalization for unstable angina or chest pain, hospitalization for heart failure requiring hospitalization, and coronary revascularization/angioplasty/stent
- Hypertension, defined as follows:

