1.1.1. Primary Objective

Primary Objective	Endpoints
To demonstrate the long-term safety of vibegron 75 mg in men with BPH with symptoms of OAB	
• Adverse Events (AEs)• Clinical laboratory assessments• Vital sign assessments• Post-void residual (PVR) urine volume• International Prostate Symptom Score (IPSS) Total Score

[figure not shown]

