7.7. Post-Void Residual (PVR) Urine Volume

PVR urine volume data will be summarized at Baseline and every visit. The summary will comprise a continuous summary at each visit, including change from baseline, and a categorical summary of PVR at the following categories: <100 mL, ≥ 100 and < 200 mL, ≥ 200 and < 350 mL, and ≥ 350 mL. All PVR data will be listed.

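### SAP 7.7 has no 300 mL cut-point and no any-time PVR summary, so no planned table is specified to count men at or above the protocol's withdrawal threshold

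*SAP*

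**What the plan says.** SAP 1.1.1 lists "Post-void residual (PVR) urine volume" among the endpoints for the primary, safety objective.

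The protocol attaches consequences to 300 mL in three places:

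- Section 2.4.2: "subjects with a single PVR volume of ≥ 300 mL or an AE of urinary retention will be withdrawn".
- Section 7.1 makes "Any occurrence of PVR volume" at or above 300 mL a reason to stop study drug.
- Section 8.4.6 repeats the withdrawal rule and uses 300 mL in defining a urinary-retention adverse event. That event needs a "raised PVR that requires intervention with clean intermittent catheterization (CIC) or temporary placement of a urinary catheter", with a PVR of at least 300 mL, or this: "subject has a PVR ≥ 200 mL and < 300 mL and the subject reports associated symptoms".

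SAP 7.7 plans a continuous and a categorical PVR summary at each visit. The categories are cut at 100, 200 and 350 mL, the upper two being "≥ 200 and < 350 mL, and ≥ 350 mL". All PVR values are listed. The only other planned PVR outputs are Table 14.3.5.1, which has no programming note, and a line plot of means.

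SAP 4.2.4.2 applies its window rules to PVR by name. Early-withdrawal and unscheduled records are slotted by study day, and where a window holds several values the one nearest the nominal day is shown.

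**The concern.** The SAP's categories do not line up with the protocol's. Values of 300 to 349 mL, which trigger withdrawal, are pooled with values of 200 to 299 mL, which on volume alone do not. The SAP gives no reason for 350 mL.

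The display rule adds a second gap. The protocol acts on any single value, and unscheduled visits are allowed, so a qualifying PVR can arise off schedule. Such a value can lose its place to an earlier scheduled value in the same window. SAP 4.2.2 sends unscheduled values to any-time on-treatment endpoints, but SAP 7.7 defines none for PVR. By contrast, SAP 7.4 and 7.5 plan maximum post-baseline summaries for laboratory tests and vital signs.

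Retention is the risk the protocol singles out in men with BPH. At stake is whether a reader of the tables can learn how many men crossed the study's own threshold.

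**Working it through.** The plan gives no figure to reproduce. The check has three parts.

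**1. What the bands reveal.** For one group at one visit, let a be the number of men in the 200 to <350 band, b the number at 350 or above, and M the maximum, which SAP 4.2.2 includes in continuous summaries. Among the tabulated records, the number at or above 300 mL is:

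- exactly b if a = 0;
- exactly 0 if b = 0 and M < 300;
- exactly 1 if b = 0, a = 1 and M ≥ 300;
- between 1 and a if b = 0, a ≥ 2 and M ≥ 300;
- between b and a + b if a ≥ 1 and b ≥ 1.

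Assumed counts for illustration:

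| a | b | M (mL) | Men at or above 300 mL |
|---|---|---|---|
| 5 | 0 | 290 | 0 |
| 5 | 0 | 340 | 1 to 5 |
| 5 | 1 | any | 1 to 6 |

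As a concrete pair, values of 210, 250, 290 and 360 mL and values of 310, 320, 340 and 360 mL both give a = 3, b = 1 and M = 360. The first set has 1 man at or above 300 mL, the second has 4. Other continuous statistics may narrow the range when numbers are small.

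**2. What the display rule leaves out.** SAP Table 4 uses the same calendar windows in both arms: Days 183–224 with nominal Day 197, and Days 225–308 with nominal Day 253. Suppose the scheduled PVR is within ±w days of nominal. A later record in that window, at least w + 1 days from nominal, always loses:

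excluded days = (224 − 197 − w) + (308 − 253 − w) = 82 − 2w, for w up to 27.

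The extension runs 28 × 7 = 196 days. The protocol window is ±4. SAP 9.3 says visit windows were widened by memo without giving the size, so 7 and 14 are assumptions.

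| w | Excluded days | Total | Share of 196 |
|---|---|---|---|
| 4 | 202–224 (23) and 258–308 (51) | 74 | 37.8% |
| 7 | 205–224 (20) and 261–308 (48) | 68 | 34.7% |
| 14 | 212–224 (13) and 268–308 (41) | 54 | 27.6% |

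For example, with 80 mL on Day 197 and 360 mL on Day 215, the table shows only 80 mL for that window. Even a value above 350 mL can drop out.

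**3. Whether another table supplies the count.**

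- Retention adverse-event tables require catheter intervention and also include symptomatic men at 200 to <300 mL.
- Protocol 8.4.6 also provides for an adverse event of residual urine volume, but this rests on the investigator's view of clinical significance and has no volume limit.
- The study-withdrawal list in Protocol 7.2 ("Reasons for discontinuation from the study include the following") has no PVR category.
- SAP 5.1 tabulates reasons for stopping drug. This would show the count only if the eCRF codes PVR as a reason, which the documents do not establish.

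**The case against.** The strongest reply is that little is lost. Safety is descriptive, so no test or decision rule changes. About 300 men are planned and every PVR value is listed, so the count can be made by hand. PVR is planned at scheduled visits, and a high value found there is normally the one displayed. The disposition and adverse-event tables may show many of these men. All of this stands. It limits the consequence but does not supply the count: each of those tables captures only part of it or depends on coding not given in the documents.

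A second objection is that the day share is not a share of men or of events. That also stands, and it should not be read as one.

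A third is that 74 days is not the full total. This is right, and it makes 74 a lower bound at ±4 days. Day 309 falls in no Table 4 window, because Week 36 ends at Day 308 and Week 52 starts after Day 309. Adding it gives 75 days (75/196 = 38.3%). Days 174–182 may also be lost: in the vibegron arm they fall in the Week 24 window, and in the placebo arm the baseline window excludes values after the first open-label dose. On that reading the total is 75 + 9 = 84 days (42.9%). If the table's footnotes instead let the next window open at the first dose, it stays at 75.

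**Conclusion.** The concern holds. No planned table is specified to count men at or above 300 mL, and the PVR table as defined cannot do so reliably. The bands and the maximum give an exact count only in the special cases above; otherwise they leave a range. Separately, an off-schedule value of any size can be absent from the table. The 74-day figure assumes that the preceding scheduled PVR was taken within ±4 days of nominal; it falls to 68 or 54 days for assumed windows of ±7 or ±14. The number of men affected cannot be derived from the documents.

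This is a reporting gap in a named primary safety endpoint, not a loss of data or a threat to the study's validity. It should be corrected.

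**What to change.** In SAP 7.7 and Table 14.3.5.1:

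- Use the categories <100, 100 to <200, 200 to <300, 300 to <350 and ≥350 mL. This keeps the existing cut and matches both volume limits in Protocol 8.4.6.
- Add a subject-level block with the same categories for the maximum PVR after the first vibegron dose, through the end of the treatment period in SAP Table 2 (last dose + 5, or end of study if earlier). Include unscheduled and early-withdrawal values.
- State how an early-withdrawal PVR taken after that period is handled, for example included and flagged.
- Define the denominator as SAF-Ext subjects with at least one PVR after the first vibegron dose. Post-baseline alone would be ambiguous for former placebo subjects, because SAP 3.1.2 and 4.3.4 set different safety baselines.

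If 350 mL was meant as a different threshold, the SAP and protocol sections must be reconciled; this review takes no view on which value is clinically right.

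The cost is SAP wording, one extra split and one row block in an existing table. The values are already collected and listed.

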7.8. IPSS Total Score

IPSS total score at Screening, Day 1, Weeks 4, 8, 12, 24, 36, and 52 for the 52-week treatment group and baseline, Week 12 and Week 28 for the 28-week treatment group will be summarized by treatment group and visit, including change from baseline.

8. COVID-19 CONSIDERATIONS

This study was conducted during the COVID-19 global pandemic. During the time period of the pandemic, it is anticipated that changes in study visit schedules, missed visits, or patient discontinuations may lead to missing information (e.g., for protocol-specified procedures). In accordance with FDA guidance on statistical considerations for clinical trials during the COVID-19 public health emergency [3], it is important to capture specific information in the case report form that explains the basis of the missing data, including the relationship to COVID-19 for missing protocol-specified information (e.g., from missed study visits or study discontinuations due to COVID-19).

The proportion of subjects with COVID-19 impact on visits will be summarized by treatment group overall and by visit. The reasons (e.g. subject acquired COVID-19, subject unable to travel due to COVID-19, investigative site closure due to COVID-19, etc.) will also be summarized. In addition, subjects who discontinued treatment due to COVID-19 will be summarized with the COVID-19 reason for discontinuation. A listing of subjects who had COVID-19 information collected will be generated which will document the date of contact, the reason for the telephone follow-up, the visit that was missed, and if any doses were missed due to IP availability.

9. CHANGE FROM ANALYSIS PLANNED IN PROTOCOL

9.1. Secondary Efficacy

CFB in average IPSS Storage score has been changed to CFB in IPSS Storage score.

9.2. Exploratory Endpoints

CFB at all URO-901-3005 or URO-901-3006 protocol-specified timepoints apart from [REDACTED] have been added for all secondary efficacy endpoints.

9.3. COVID-19 Considerations

The COVID-19 global pandemic began during the conduct of the study. The recommended impact analysis was therefore added to the SAP, as the operational change of increased visit windows had been communicated via study memo with no protocol amendment.

9.4. Physical Examination

Physical examination was removed from primary objectives; any clinically significant finding is reported by the investigator as an adverse event and is summarized with adverse events. Physical examination results will be only listed.

11. APPENDIX

11.1. Table of Contents for Data Display Specifications

11.1.1. Output Tables

Table 9: List of Output Tables

Title		Population	Programming notes
Study Population			
14.1.1.1	Subject Disposition	Screened	Include two sections: screened, treated
14.1.1.2	Enrollment by Country and Investigator	SAF-Ext	
14.1.2.1	Major Protocol Deviations	FAS-Ext	
14.1.2.2	Reasons for Exclusion from Analysis Sets	SAF-Ext	
14.1.3.1	Subject Demographic and Baseline Characteristics	SAF-Ext	
14.1.3.2	Subject Demographic and Baseline Characteristics	FAS-Ext	
14.1.3.3	Subject Demographic and Baseline Characteristics	FAS-Ext-I	
14.1.3.4	Subject Demographic and Baseline Characteristics	PPS-Ext	
14.1.3.5	Subject Demographic and Baseline Characteristics	PPS-Ext-I	
14.1.3.8	Other Baseline Characteristics	FAS-Ext	
14.1.3.9	Other Baseline Characteristics	FAS-Ext-I	
14.1.3.10	Other Baseline Characteristics	PPS-Ext	

Title		Population	Programming notes
14.1.3.11	Other Baseline Characteristics	PPS-Ext-I	
14.1.4	Medical History	SAF-Ext	
14.1.5.1	Prior Non-Overactive-Bladder (OAB) Medication	SAF-Ext	
14.1.5.2	Prior Overactive Bladder (OAB) Medication	SAF-Ext	
14.1.6.1	Non-OAB Concomitant Medication	SAF-Ext	
14.1.6.2	OAB Concomitant Medication	SAF-Ext	
14.1.7.1	COVID-19 Impact	SAF-Ext	
Efficacy Endpoints			
Secondary Efficacy Endpoints			
14.2.1.1	Average Daily Number of Micturition Episodes	FAS-Ext	Descriptive statistics, include CFB
14.2.1.2	Change from Baseline in Daily Average Number of Micturition Episodes (MMRM)	FAS-Ext	Include all intervals, but present Week 52 first
14.2.1.3	Change from Baseline in Daily Average Number of Micturition Episodes (MMRM)	PPS-Ext	Include all intervals, but present Week 52 first
14.2.2.1	Average Daily Number of Urgency Episodes	FAS-Ext	Descriptive statistics, include CFB
14.2.2.2	Change from Baseline in Average Daily Number of Urgency Episodes (MMRM)	FAS-Ext	Include all intervals, but present Week 52 first
14.2.2.3	Change from Baseline in Average Daily Number of Urgency Episodes (MMRM)	PPS-Ext	Include all intervals, but present Week 52 first
14.2.3.1	Average Number of Nocturia Episodes per Day	FAS-Ext	Descriptive statistics, include CFB

Title		Population	Programming notes
14.2.3.2	Change from Baseline in Average Number of Nocturia Episodes per Day (MMRM)	FAS-Ext	Include all intervals, but present Week 52 first
14.2.3.3	Change from Baseline in Average Number of Nocturia Episodes per Day (MMRM)	PPS-Ext	Include all intervals, but present Week 52 first
14.2.4.1	Average Daily Number of Urge Urinary incontinence Episodes	FAS-Ext-I	Descriptive statistics, include CFB
14.2.4.2	Change from Baseline in Average Daily Number of Urge Urinary incontinence Episodes (MMRM)	FAS-Ext-I	Include all intervals, but present Week 52 first
14.2.4.3	Change from Baseline in Average Daily Number of Urge Urinary incontinence Episodes (MMRM)	PPS-Ext-I	Include all intervals, but present Week 52 first
14.2.5.1	International Prostate Symptom Score (IPSS) Storage Score	FAS-Ext	Descriptive statistics, include CFB
14.2.5.2	Change from Baseline in International Prostate Symptom Score (IPSS) Storage Score (MMRM)	FAS-Ext	Include all intervals, but present Week 52 first
14.2.5.3	Change from Baseline in International Prostate Symptom Score (IPSS) Storage Score (MMRM)	PPS-Ext	Include all intervals, but present Week 52 first
14.2.6.1	Average Volume Voided per Micturition	FAS-Ext	Descriptive statistics, include CFB
14.2.6.2	Change from Baseline in Average Volume Voided per Micturition (MMRM)	FAS-Ext	Include all intervals, but present Week 52 first
14.2.6.3	Change from Baseline in Average Volume Voided per Micturition (MMRM)	PPS-Ext	Include all intervals, but present Week 52 first
Other Efficacy and PROs Endpoints			

Title		Population	Programming notes
14.2.7.1	International Prostate Symptom Score (IPSS) Quality of Life Score	FAS-Ext	Descriptive statistics, include CFB
14.2.7.2	International Prostate Symptom Score (IPSS) Voiding Score	FAS-Ext	Descriptive statistics, include CFB
14.2.8.1	Urgency Episodes per Day 50% Responder Analysis	FAS-Ext	Descriptive statistics
14.2.9.1	Change from Baseline in Average Number of Total Incontinence Episodes per Day	FAS-Ext-I	Descriptive statistics, include CFB
14.2.9.2	Urge Urinary Incontinence Episodes per Day 75% Responder Analysis	FAS-Ext-I	Descriptive statistics
14.2.10.1	[REDACTED]	FAS-Ext	[REDACTED]
14.2.11.1	[REDACTED]	FAS-Ext	[REDACTED]
14.2.11.2	[REDACTED] Crosswalk Index Value	FAS-Ext	[REDACTED]
14.2.11.3	[REDACTED] VAS Value	FAS-Ext	[REDACTED]
14.2.12.1	Overall Symptom Severity Bladder Symptoms Based on [REDACTED]	FAS-Ext	[REDACTED]

Title		Population	Programming notes
14.2.12.2	Overall Symptom Control over Bladder Symptoms Based on [REDACTED]	FAS-Ext	Repeat 14.2.12.1
14.2.12.3	Overall Symptom Frequency Based on [REDACTED]	FAS-Ext	Repeat 14.2.12.1
14.2.12.4	Overall Urgency-Related Leakage over Bladder Symptoms Based on [REDACTED]	FAS-Ext-I	Repeat 14.2.12.1
14.2.12.5	Overall Change of Bladder Symptoms Based on [REDACTED]	FAS-Ext-I	Categorical summary
14.2.12.1	[REDACTED] Domain Scores and Overall Satisfaction Score	FAS-Ext	Include CFB
Safety Endpoints			
14.3.1.1.1	Treatment Exposure	SAF-Ext	
14.3.1.1.1	Treatment Exposure	FAS-Ext	
14.3.1.2	Treatment Compliance	SAF-Ext	
14.3.1.3	Treatment Compliance	FAS-Ext	
Adverse Events			
14.3.2.1	Overall Summary of Treatment Emergent Adverse Events	SAF-Ext	
14.3.2.2	Treatment Emergent Adverse Events by System Organ Class and Preferred Term	SAF-Ext	Descending frequency of SOC and PT
14.3.2.3	Treatment-Related Treatment Emergent Adverse Events by Preferred Term	SAF-Ext	Descending frequency of preferred term

Title		Population	Programming notes
14.3.2.4	Treatment-Emergent Adverse Events by Preferred Term and Maximum Intensity	SAF-Ext	Descending frequency of preferred term
14.3.2.5	Treatment Emergent Adverse Events with Grade \geq 3 by Preferred Term	SAF-Ext	Descending frequency of preferred term
14.3.2.6	Treatment-Related Emergent Adverse Events with Grade \geq 3 by Preferred Term	SAF-Ext	Descending frequency of preferred term
14.3.2.7	Treatment-Emergent Adverse Events occurring in \geq 2% subjects by Preferred Term	SAF-Ext	Descending frequency of preferred term
14.3.2.8	Serious Treatment Emergent Adverse Events by Preferred Term	SAF-Ext	Descending frequency of preferred term
14.3.2.9	Treatment-Related Serious Treatment Emergent Adverse Events by Preferred Term	SAF-Ext	Descending frequency of preferred term
14.3.2.10	Treatment Emergent Adverse Events Leading to Discontinuation from Study Treatment by Preferred Term	SAF-Ext	Descending frequency of preferred term
14.3.2.11	Fatal TEAEs by Preferred Term	SAF-Ext	Descending frequency of preferred term
14.3.2.12	Treatment Emergent Adverse Events of Special Interest by Preferred Term	SAF-Ext	Descending frequency of preferred term
14.3.2.13	Treatment-Related Treatment Emergent Adverse Events of Special Interest by Preferred Term	SAF-Ext	Descending frequency of preferred term
14.3.2.14	Non-Fatal Treatment-Emergent Adverse Events by Preferred Term	SAF-Ext	Descending frequency of preferred term
14.3.2.15	Hypertension Treatment Emergent Adverse Events by Preferred Term, and Pre-Existing Hypertension	SAF-Ext	Descending frequency of preferred term
14.3.2.16	Hypertension Treatment Emergent Adverse Events by Preferred Term, and Baseline Hypertension	SAF-Ext	Descending frequency of preferred term
14.3.2.17	Listing of Deaths	SAF-Ext	

Title		Population	Programming notes
14.3.2.18	Listing of Treatment Emergent Serious Adverse Events	SAF-Ext	
14.3.2.19	Listing of Treatment Emergent Adverse Events Leading to Withdrawal or Interruption of Study Treatment	SAF-Ext	
14.3.2.20	Listing of TEAEs of Special Interest	SAF-Ext	
Safety Labs			
14.3.3.1	Hematology Laboratory Parameters	SAF-Ext	Include observed and CFB
14.3.3.2	Clinical Chemistry Laboratory Parameters	SAF-Ext	Include observed and CFB
14.3.3.3	Urinalysis Laboratory Parameters	SAF-Ext	Include observed and CFB
14.3.3.4	Summary of Other Laboratory Parameters	SAF-Ext	
14.3.3.5	Abnormal Classification of Hematology Laboratory Parameters	SAF-Ext	
14.3.3.6	Abnormal Classification of Clinical Chemistry Laboratory Parameters	SAF-Ext	
14.3.3.7	Abnormal Classification of Urinalysis Laboratory Parameters	SAF-Ext	
14.3.3.8	Abnormal Classification Summary of Other Laboratory Parameters	SAF-Ext	
14.3.3.9	Shift Table of L/N/H Classification for Hematology Laboratory Parameters	SAF-Ext	
14.3.3.10	Shift Table of L/N/H Classification for Chemistry Laboratory Parameters	SAF-Ext	
14.3.3.11	Maximum Post-baseline ALT and AST vs. Maximum Post-baseline Bilirubin	SAF-Ext	

Title		Population	Programming notes
14.3.3.12	Listing of Subjects who Potentially Met Hy’s Law	SAF-Ext	
14.3.3.13	Summary of Liver Function Laboratory Findings	SAF-Ext	
Vital Signs			
14.3.4.1	Vital Sign Parameters	SAF-Ext	Include all observed and CFB
14.3.4.2	Vital Sign Parameter Change from Baseline Shifts at 3 Consecutive Visits	SAF-Ext	SBP, DBP and PR
14.3.4.3	Vital Sign Parameter Change from Baseline Shifts at Week 52	SAF-Ext	SBP, DBP and PR
14.3.4.4	Vital Sign Parameter Maximum Post-Baseline Change from Baseline	SAF-Ext	SBP, DBP and PR
Other			
14.3.5.1	Post-Void Residual Volume	SAF-Ext	
14.3.6.1	Total IPSS score	SAF-Ext	
14.3.7.1	Physical Examination Shift from Baseline	SAF-Ext	

